### 3.8 Justification of choice of study population

The choice of the study population was determined by the goal of the study. The intended purpose of the study is to compare the current standard of fitting to the new self-directed device. Therefore, only participants that are hearing impaired with a hearing loss that is indicated for amplification will be included. Experienced hearing aid users will be excluded because they have experience with the standard testing and fitting procedure that will bias their judgement of the two processes used for this particular study.

Test subjects will be chosen as they appear in either the Bern Audika clinic or the Thun Audika clinic for appointments that they have made for an initial hearing test. No employees of Bernafon or family members of employees will be included in the study. The participants will have the study explained and be consented before any trial activities take place. If they would like to participate, they will sign the consent form along with the investigator and trial activities for day 0 can begin. All trial activities including the initial hearing test to determine candidacy will take place at either the Bern or Thun Audika clinics.

If they do not wish to participate in the study they can cancel the appointment or they can continue with the normal hearing aid purchasing process.

Testing normal hearing participants would not contribute information to this study. It would not be ethical to fit normal hearing people with hearing aids. Test participants must be able to sign and understand the consent form otherwise they will not be included.

Vulnerable participants and those incapable of making their own judgments will not be included.

For emergency situations, the following applies:

-The standard procedure is to recommend that a subject see the ENT with whom they have an established relationship. If a subject does not have an ENT then it is agreed with [name] (Inselspital, Bern) that, if necessary, subjects from this trial could be referred to him.

# 4. STUDY OBJECTIVES

### 4.1 Overall Objective

The purpose of this study is to compare the performance of the IMD to the RMD. The study aims to provide a final validation and quality control of the IMD before it is released for sales.

#### 4.2 Primary Objective

The study seeks primarily to determine if the subjective benefit of the hearing aids fitted with the IMD is as good as the RMD. Does one fitting method provide a psychological effect that influences the participants? As a second primary objective the study seeks to proactively determine if there is any unknown and/or unwanted behavior from the IMD. The study seeks to validate that the performance of the IMD is not inferior to the RMD.

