### 11.1 Hypothesis

Both devices will have the same electro-acoustical performance; however, it is suspected that changing the fitting procedure might influence the subjective benefit for the hearing aid user. Research suggests that placebo effect might impact hearing aid trials (Dawes et al., 2013) and that clinician behavior might also modify the perceived benefit of hearing aids (Naylor et al., 2015). The designed test will investigate the potential effect of the IMD compared to the RMD on first time users.

The test should answer the following research questions:

- Narrative effect of fitting procedure: Do different fitting procedures lead to differences in perceived benefit with hearing aids despite similar electro-acoustical performance? (Questionnaires)
- 2. Self-administrated audiometry: Is AMTAS self-administrated screening equivalent to standard clinical procedure? (hearing loss thresholds)

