### 11.4 Planned Analyses

The analysis and documentation will be done by the statistician using R (latest available and validated version) downloaded from the official Comprehensive R Archive Network (https://cran.r-project.org/). R-Studio IDE will be used to integrate the analysis to the report. R provides adequate packages for descriptive statistics (base, stats, and Rmisc), data visualisation (ggplot2), mixed effect models (Imer, ImerTest, and nIme), and principal component analysis (FactoMineR).

A linear mixed effect regression will be used on the IOI-HA questionnaire, chi-squared distribution on the preference test and a paired t-test on hearing thresholds. The principal component analysis will be made on different outcomes and explanatory variables combinations.

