#### 11.4.2 Primary Analysis

The narrative effect on the subject perception of the end user will be measured using a standardized questionnaire, the IOI-HA, and a custom product questionnaire. The questionnaires will be administered twice during the study, once after each field trial period. The responses for the IMD will be compared with those for the RMD. At the last visit the subjects will complete a preference questionnaire based on the Naylor et al. (2015).

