2.1 Primary outcomes

The perceived benefit will be measured with:

- a. the IOI-HA questionnaire and its official translation into German (Cox et al., 2002)
- b. a custom questionnaire based on reference article from Naylor et al. (2015).

These two questionnaires were used in the reference article from Naylor et al. (2015) to measure the effect of narrative embodied in the hearing aid fitting process. Even current research question addresses another aspect of the fitting process, these tools have shown a potential to detect changes in the investigated processes.

IOI-HA questionnaire

Perceived benefit of amplification assessed with 7 questions on a 5 points scale (maximum score 35). Indication from reference study found an effect of fitting process between the preferred and less preferred possibility:

- significant 3.2 scale points and an effect size of 0.68 with experience hearing aid users (n = 24),
- non-significant 0.5 scale points with first time hearing aid users (n = 16).

Custom questionnaire

From the reference study, the questionnaire will directly ask about the preference (much better/slightly better/no difference), the certainty of preference (10 points VAS), and the reason (multiple choice: sound quality, speech intelligibility, listening effort, comfort, loudness, other).

- Fitting procedures: no significant difference between both fitting procedures for first time and experienced hearing aid users,
- Placebo effect: 20 out of 24 indicated a difference with a mean certainty of 7.9/10 for the experienced users group. 14 out of 16 indicated a difference with a mean certainty of 7.0/10 for the first time users group

Order effect

From the reference study, test order might play a different role for first time or experienced users:

- No order effect was found with the experienced hearing aid users,
- A highly significant test order effect in favor for the second tested hearing aid was found for the first time users.

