4.1 Analysis methods

Linear mixed effect regression will be used on the IOI-HA questionnaire, chi2 distribution on the preference test and paired t-test on audiometrical thresholds. Principal component analysis will be made on different outcomes and explanatory variables combinations.

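### Protocol 4.2 sets an 'as good as' and 'not inferior' objective, but the IOI-HA is analysed only for a difference, with no margin or confidence-interval rule

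*Protocol*

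**What the plan says.** Protocol 4.2 (Primary Objective) opens with "The study seeks primarily to determine if the subjective benefit of the hearing aids fitted with the IMD is as good as the RMD". It then asks whether one fitting method has a psychological effect, names a second primary objective about unwanted behaviour of the IMD, and closes with "The study seeks to validate that the performance of the IMD is not inferior to the RMD". The introduction to protocol section 11 adds that the IMD is not expected to outperform the RMD.

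The statistical sections ask a different question. Protocol 11.1 has "Do different fitting procedures lead to differences in perceived benefit with hearing aids despite similar electro-acoustical performance", and SAP 1.1 asks the same. Protocol 11.4.2 says only "The responses for the IMD will be compared with those for the RMD". The method is named in protocol 11.4 and again in SAP 4.1: "Linear mixed effect regression will be used on the IOI-HA questionnaire, chi2 distribution on the preference test and paired t-test on audiometrical thresholds". SAP 1.3 makes investigator a random effect and adds an investigator-by-treatment interaction; protocol 11.2 and SAP 3.1 set four investigators.

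Neither document gives an IOI-HA margin, a rule for the confidence interval or a success criterion. The one power figure adopted for the sample size (0.82, protocol 11.2 and SAP 3.2) belongs to the preference chi-square test. The synopsis calls the analysis exploratory only, with 24 to 40 participants.

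**The concern.** A claim that one method is as good as another needs an upper bound on how much worse it could be. A test for a difference gives no such bound: when it is non-significant, the data may fit no deficit, a small deficit or a sizeable one. Without a margin or interval rule, the planned IOI-HA analysis can answer the narrative-effect question in protocol 11.1 but not the *as good as* sentence in 4.2.

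This matters because protocol 4.1 describes the study as final validation before sale. With few participants, non-significance is a likely outcome for modest deficits, and noisier or smaller data make it likelier. A reader who takes the wording of 4.2 at face value could treat that outcome as support for release.

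**Working it through.** **1. The plan's own power figure.** For the three-category preference test, λ = N·w² = 24 × 0.65² = 10.14. With 2 df and α = 0.05, the noncentral chi-square gives power 0.821 against the stated 0.82. The two-category option, 24 × 0.6² = 8.64 with 1 df, gives 0.836 against 0.84. Both reproduce. Neither concerns the IOI-HA.

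**2. Inputs for the IOI-HA.** SAP 2.1 gives a maximum score of 35. From the reference study it reports 3.2 points with effect size 0.68 in 24 experienced users, and a non-significant 0.5 points in 16 first-time users. Treating 0.68 as mean difference over SD of differences, SD = 3.2/0.68 = 4.71. This is an assumption, so I also show 3 and 6.

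**3. Precision under a simple paired test.** SE = SD/√n = 4.71/√24 = 0.961. Half-width = t(0.975; 23) × SE = 2.069 × 0.961 = 1.99 points. It is 1.27 at SD 3 and 2.53 at SD 6. At n = 40 and SD 4.71 it is 1.51.

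**4. Chance that a true IMD deficit is non-significant** (two-sided 0.05, noncentral t with noncentrality deficit/SE):

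| True deficit (points) | n=24, SD 3 | n=24, SD 4.71 | n=24, SD 6 | n=40, SD 4.71 |
|---|---|---|---|---|
| 0.5 | 88% | 92% | 93% | 90% |
| 1 | 65% | 83% | 88% | 74% |
| 1.5 | 35% | 68% | 78% | 50% |
| 2 | 12% | 49% | 65% | 25% |
| 2.5 | 3% | 30% | 50% | 9% |
| 3.2 | 0.1% | 11% | 29% | 1% |

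The deficit missed half the time is 1.97 points at n = 24 and SD 4.71 (1.25 at SD 3, 2.5 at SD 6), and about 1.5 points at n = 40.

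**5. Effect of the planned model.** Suppose the random investigator-by-treatment term with four investigators leaves about 3 df for the treatment effect, and that effect varies between investigators with SD τ. Then SE = √(4.71²/24 + τ²/4) and t(0.975; 3) = 3.182.
- τ = 0: SE 0.961, half-width 3.1 points.
- τ = 1: SE 1.083, half-width 3.4 points.

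The power of the difference test then falls from 89% to between 52% and 61% at 3.2 points, and from 51% to between 26% and 31% at 2 points. The 3 df and the range of τ are assumptions; the documents give neither.

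**6. What a margin would demand.** Paired non-inferiority, one-sided 0.025, true difference 0, SD 4.71, simple paired test:

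| Margin (points) | Power at 24 | Power at 40 | N for 80% power |
|---|---|---|---|
| 1 | 17% | 26% | 176 |
| 2 | 51% | 75% | 46 |
| 2.5 | 70% | 91% | 30 |
| 3.2 | 89% | 99% | 19 |

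These powers are optimistic if step 5 applies. The margins are illustrations, not proposals.

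**The case against.** The strongest reply is that this is a self-declared exploratory study. The synopsis says so, and protocol 11.2 and SAP section 3 say the literature cannot support a confirmatory analysis. No section says that a non-significant IOI-HA result counts as success or triggers release. Section 4.2 is also mixed: its psychological-effect question runs in both directions and the mixed model does address it, while the *not inferior* sentence speaks of performance and follows the objective on unwanted behaviour. Only the *as good as* sentence is explicitly about subjective benefit.

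Most of this stands, and it limits the point. A reader might infer that the plan would usually pass off a real IMD deficit as success. The documents do not support that: they contain no such rule, and *usually* holds only for deficits below about 2 points at 24 participants. A 3.2-point deficit, the only significant IOI-HA effect the SAP cites, is missed about 11% of the time under a simple paired test.

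A reader might also infer that 3.2 points is a ready margin with 89% power. SAP 2.1 reports it as an observed contrast between preferred and less preferred fittings in experienced users, whom this trial excludes. It is not a tolerable loss, and the 89% does not allow for the interaction term.

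The exploratory label does not remove the mismatch. Section 4.2 still speaks of validating non-inferiority, and nothing planned for the IOI-HA can do that.

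**Conclusion.** The *as good as* objective, and *not inferior* so far as it covers subjective benefit, have no matching IOI-HA analysis. A non-significant difference could not support either phrase and could be misread as doing so. Under a simple paired test with SD 4.7, deficits below about 2 of 35 points at 24 participants, or about 1.5 at 40, would more often than not be non-significant. Over SD 3 to 6 the threshold at 24 participants is 1.25 to 2.5 points. The half-width of about 2.0 points could become 3.1 to 3.4 under the planned random interaction.

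The sizes rest on an SD from experienced users and a different contrast, and on 0.68 being a paired effect size. If 0.68 was standardised by the raw-score SD, the paired SD would be 5.57, 4.71 or 3.65 at within-person correlations of 0.3, 0.5 or 0.7. The mismatch itself rests on none of these assumptions. Severity: should-fix.

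**What to change.** Keep the mixed model. In protocol 11.4.2 and SAP 4.1, state that the IMD minus RMD difference in IOI-HA total will be reported from that model with a two-sided 95% CI, and that a non-significant difference will not be read as *as good as* or *not inferior*.

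Then choose one of two routes before the data are analysed:
- **Set a margin.** Allow the claim only if the lower confidence limit lies above a margin the sponsor justifies in advance. Check feasibility at 24 to 40 participants under the planned model, including the investigator-by-treatment term.
- **Drop the claim.** In keeping with the exploratory label, delete both phrases from 4.2 and report the largest deficit the interval does not exclude.

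The reporting rule and the deletion change wording only and need no extra participants. The margin route may need more: even with the simple paired test, a 2-point margin needs about 46 for 80% power, above the cap of 40. The price in either case is a conclusion that is harder to reach or more modest.

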#### 4.3 Secondary Objectives

Secondary objectives are to assess the performance of the hearing aids after being programmed by both fitting methods. The hearing aids will be the same electro-acoustically and should provide equivalent aided benefit.

#### 4.4 Safety Objectives

The study aims to validate the overall implementation of the IMD. The study will test for unexpected behavior from the IMD and new risk factors to ensure safety of the devices before they are released to the market.

# 5. STUDY OUTCOMES

### 5.1 Primary Outcome

The primary outcome variable will be the subjective benefit of the hearing aids measured with a standardized questionnaire: the International Outcome Inventory for Hearing Aids (IOI-HA) and a custom questionnaire based on the questionnaire used in the Naylor et al. (2015) study. A comparison will be made between the subjective benefit measured with the hearing aids fitted with the control (RMD), and with the test device (IMD).

### 5.2 Secondary Outcomes

The secondary outcome variables are the audiometry as measured with the standard test and with the automated system. The data analysis will focus on the hearing threshold differences with both procedures in a nested model: ear-participant-investigator.

Additionally data logging from the hearing aids will be recorded as an indication of hearing aid use. The data will be averaged from each ear. The following data will be used:

1. Daily usage in hours per day,

2. Acoustical environment in percentage for the following listening environments: quiet, speech in quiet, speech in noise, and noise.

### 5.3 Other Outcomes of Interest

Explanatory variables include speech intelligibility testing using a multi-syllable word test called the Freiburger Sprachverständnistest (FST). This test will measure the objective benefit (difference from unaided and aided) from the hearing aids as fitted with the RMD and the IMD. Also the perceived handicap associated with hearing impairment may influence the perceived benefit from the hearing aids. The Gothenburg Profile (GP) will be used to quantify perceived handicap and the influence it may have on the primary outcome. A custom packaging questionnaire specific to hearing aids will test the usability of the packaging.

### 5.4 Safety Outcomes

The test participants will be asked whether anything unexpected that occurs during the field trial periods. Unexpected things include feedback or whistling from the device, unexpected sounds or artefacts from the device, discomfort, muting or shutting off of the device in mid-use, unexplained warning signals or beeping from the device, loud sounds, and occlusion. The information provided from the field trial will alert Bernafon to the potential for safety risks that should be addressed before the product is released to the market.

# 6. STUDY DESIGN

### 6.1 General study design and justification of design

This is a controlled, randomized, open label, cross-over, comparative clinical investigation conducted at two sites within Canton Bern, Switzerland.

The exploratory study is based on a population of hearing impaired people that have hearing loss appropriate for the hearing aids.

As a control, the RMD will be used to fit the hearing aids as well as the IMD. Additionally, a control situation will be implemented by using an unaided test condition in laboratory speech testing.

There is no placebo or "fake" device that does not provide amplification. A randomized cross-over design will be used with one group using the device programmed with the RMD first and the other using the device programmed with the IMD and then switching. The testing will be unblinded as the subjects can clearly see a difference between fitting methods. Although two hearing tests will be completed (standard audiometry and IMD screening), the hearing aids will be programmed only with the IMD screening results in order to reduce variability in the analysis of the results. Therefore, the hearing aids will be acoustically programmed the same, but this will not be explained to the participants.

The same randomized test order will be used to test in a simulated environment. At the end of the field test period the participants will return to the clinic. They will be given a speech test in the unaided condition and the aided condition with the hearing aids as they have worn them for the previous 10 days. They will then be fit with the other method (whichever they did not have in the first round), and then have speech testing again in the aided and unaided condition at the end of the field test period.

The participants will be expected to participate for approximately 1 month for a combination of field tests and lab tests. For lab tests they will not spend more than 1.5 hours in the clinic for testing. They will be expected to come for 3 visits in total. Field trial periods will not last more than 10 +/-5 days.

The sequence will begin with the screening visit which will also be the first intervention visit if they satisfy the inclusion criteria and if they choose to join the study. The entire test procedure will be explained, and they will be given a Patient Informed consent form to read which will need to be signed, dated, and returned before any trial procedures begin.

Subjects will be given questionnaires to complete with all field test periods. After they have completed all appointments the subjects will complete a preference questionnaire to determine their preference between the IMD and RMD. They will also be given the option to purchase hearing aids from the clinic. If they purchase the hearing aids they will receive all follow-up care at that specific clinic.

### 6.2 Methods of minimi sing bias

#### 6.2.1 Randomisatio n

For the cross-over design, the participants will be divided into two groups. One group will begin the trial with hearing aids programmed with the IMD and the other group will begin the trial with hearing aids programmed with the RMD. Each field trial will last for 10 days (+/-5d). Then they will return to the clinic for an appointment. The allocation to the groups will be randomized using a block randomization method in groups of four. They will be assigned as they appear in the clinics for their appointments. All investigators at the sites should be assigned an equivalent number of participants.

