Number of Participants with Rationale:	There will be an exploratory analysis of data only. The total number of participants will be a minimum of 24 (no more than 40), and the explanation for this sample size is as follows:
	A literature search about this tested topic does not provide enough strong references to build a confirmatory analysis. It seems that results might be strongly influenced by the inclusion criteria (first time vs experienced hearing aid users) or test design (cross-over, multi-investigator, or between group designs). There is no article to our knowledge that includes a multi-investigator effect in the test design when looking at the effect of different fitting procedures. Adding a treatment interaction term seems to be mandatory if this trial wants to determine the effect that different investigators may have. Each investigator shall treat the same amount of subjects.
	The 24-40 subjects will participate in 2 field studies, but randomized into different fitting/intervention groups with half the number of subjects in each group.
Study Duration:	Approximately 3 months
	The screening of the participants will begin in February of 2018 and the final data collection appointments will occur in April 2018.
Study Sched ule:	The first participant is expected to begin in February 2018.
	The last participant is expected to finish the testing in April 2018.
Investigator(s):	[name], Research Audiologist, Doctor of Audiology
	[name]
	[contact] [contact]
Study Centre(s):	The testing will be performed at two clinical sites in canton Bern, Switzerland.
Statist ical Consider ations:	The analysis and documentation will be performed by the statistician using the latest validated R version with R Studio as IDE. Appropriate data analysis will be performed with parametric and non-parametric tests on questionnaire outcomes, hearing threshold measures, and speech test scores.

GCP Statement:	This study will be conducted in compliance with the protocol, the current version of the Declaration of Helsinki, the ICH-GCP or ISO EN 14155 (as far as applicable) as well as all national legal and regulatory requirements.
	Tal as applicable) as well as all flational legal and regulatory requirements.

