#### 6.2.2 Blind ing procedu res

There will be no blinding as it is impossible to hide the programming method because the differences are very distinct.

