### 7.1 Eligibil ity criteria

Participants fulfilling all of the following inclusion criteria are eligible for the study:

- All classifications of hearing loss (sensorineural, conductive, combined)
- If the hearing loss is conductive or combined it must be approved for amplification by a physician
- All shapes of hearing loss (flat, sloping, reverse slope, notch)
- Hearing loss severity ranging from mild to severe
- First time hearing aid users
- German speaking
- Both genders
- Ages 18 and older
- Ability and willingness to sign the consent form

The presence of any one of the following exclusion criteria will lead to exclusion of the participant:

- Contraindications for amplification
- Experienced or current hearing aid users
- Active ear disease
- Inability to follow the procedures of the study due to language problems, psychological disorders, dementia, or other cognitive problems of the participant,
- A reduced mobility making them unable to attend weekly study appointments
- A reduced ability to describe auditory impressions and the usage of the hearing aids
- Uncooperative so that it is not possible to record a valid pure tone audiogram
- A strongly reduced dexterity
- Central hearing disorders
- Bernafon employees
- Family members of Bernafon employees

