### 7.3 Assignment to study group s

The participants are randomized by a block assignment as they appear at the trial sites. There will be 24-40 subjects. The test condition order will be randomized using a 2-factor randomization with a 6 block design. The first factor is the investigator with 4 levels, and the second factor is the test order with 2 levels. This will minimize the bias created when one test condition is tested in the first or last position all of the time.

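### Order is allocated in a disclosed fixed block of four, in an open trial with no described concealment, so investigators may be able to foresee some assignments; the likely effect on the results is modest.

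*Protocol*

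**What the plan says.** - Protocol 6.2.1: "The allocation to the groups will be randomized using a block randomization method in groups of four". The next step is "They will be assigned as they appear in the clinics for their appointments".
- Protocol 7.3 describes the scheme differently: "The test condition order will be randomized using a 2-factor randomization with a 6 block design". It adds: "The first factor is the investigator with 4 levels, and the second factor is the test order with 2 levels". It does not say whether blocks run within investigator, within site or across the whole trial, or whether the 6 is a block size or a number of blocks.
- Protocol synopsis: participants are "randomized into different fitting/intervention groups with half the number of subjects in each group", so the ratio is 1:1.
- Protocol 6.2.2: "There will be no blinding as it is impossible to hide the programming method because the differences are very distinct".
- Protocol 9.3.1 and 8.2.2: the site investigator explains the trial, countersigns consent, and carries out or oversees the first visit, at which eligibility is settled. The investigator also fits the hearing aids.
- Protocol 12.1.2: the protocol is kept in the investigator's file, so the block size is known at the sites.
- Protocol 7.1: some exclusions rest on judgement, for example "A reduced ability to describe auditory impressions and the usage of the hearing aids".
- SAP 2.1, on the reference study: "A highly significant test order effect in favor for the second tested hearing aid was found for the first time users".

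Neither document names a list generator, a list holder, a concealment method or a release step.

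**The concern.** With a fixed block of known size and no blinding, anyone who has seen the earlier assignments in a block can sometimes work out the next one. Here that person may also be deciding whether the next candidate enters. The judgement-based exclusions leave some room to act on that knowledge. So might the already screened back-up participants in Protocol 7.4, although 11.5 says dropouts are not replaced, so their use is unclear.

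In this cross-over, stable differences between participants cancel, because each person is compared with themselves. A difference between the two order groups in how much people change from the first to the second period does not cancel: half of it enters the IMD-RMD estimate. The trial enrols only first-time users, the group in which the SAP reports a strong order effect, so change between periods is to be expected.

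**Working it through.** The documents give no predictability figure to reproduce. Their stated power of 0.82 recomputes to 0.821, but plays no part here.

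**Inputs.** Block of 4, ratio 1:1 (Protocol 6.2.1, synopsis). Four investigators with 6 to 8 participants each (Protocol 11.2). Total 24 to 40 (synopsis), so 10 each at the upper limit.

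**Assignments known with certainty, block of 4.** The fourth is always known. The third is known when the first two match, which has probability 1/3. The expected number is 1 + 1/3 = 4/3 per block, or 33.3%. Within a single block the share is 25% (two thirds of blocks) or 50% (one third of blocks).

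**Best-guess rate, block of 4.** [2 + (2^4/C(4,2) - 1)/2]/4 = [2 + 0.833]/4 = 0.708. An unpredictable list gives 0.50.

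**By structure, if blocks run within investigator:**
- 6 each (one full block and half of another): certain (4/3)/6 = 22.2%. In the half block, the second position is guessed correctly 2/3 of the time. The best guess is therefore (2.833 + 0.5 + 0.667)/6 = 0.667.
- 8 each (two full blocks): certain (8/3)/8 = 33.3%, best guess 0.708.
- 10 each: certain (8/3)/10 = 26.7%.
- If 7.3 means a block size of 6, with complete blocks: certain 25.0%, best guess [3 + (64/20 - 1)/2]/6 = 0.683.

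**One common list, n = 24, each investigator seeing only their own assignments (simulation):** about 1.3% certain, best guess 0.53. If assignments are shared within two equal groups, about 7.2% are certain.

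**Bias if entry is steered (illustration; the documents give no figure).** Suppose each investigator shifts the expected period difference of the next entrant by ν SD towards the order judged more likely, and makes no shift when the two orders are equally likely. With best-guess rate g, correct guesses exceed wrong ones by 2g - 1. The order groups then differ by 2ν(2g - 1), and half of that enters the treatment estimate:

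bias = ν(2g - 1), in SDs of the period difference.

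| Structure | g | ν = 0.5 | ν = 0.25 |
|---|---|---|---|
| Within investigator, 6 each | 0.667 | 0.17 | 0.08 |
| Within investigator, 8 each | 0.708 | 0.21 | 0.10 |
| Common list, own assignments only | 0.53 | 0.03 | 0.015 |

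Simulation of the within-investigator cases gives the same bias (0.166 and 0.206 at ν = 0.5). A nominal 5% test then rejects about 10% of the time with 4 x 6, and 17% to 20% with 4 x 8 across repeated simulations. If the direction of steering varies at random between investigators, the mean bias is zero and rejection is about 5% to 7%. If investigators act only on assignments that are certain, rejection is about 8% and 14%. With no steering there is no bias.

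**The case against.** The strongest reply is that predictability depends on a structure the documents leave open. SAP section 3 says participants are randomly assigned to one of four investigators who can work at both sites, and no passage says that blocks run within investigator. This stands. It is why the certain share has to be given as a range from about 1% to 33%. A reader might take one third as a general figure or a ceiling. It is neither: it is the average for complete blocks whose earlier assignments are all visible to the person enrolling.

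The second reply is that the procedures already limit steering. A call centre recruits and books participants (Protocol 7.2). Protocol 9.3.1 puts consent, audiometry, eligibility and the Gothenburg form before the fitting, and refers to a randomisation plan that is not among the documents. This stands in part: the visit sequence is close to what is needed, but the documents do not say when the order becomes known.

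Third, a reader might infer from the SAP's order effect that bias is to be expected. The documents do not support that. The reported effect is an average, and a cross-over using both orders can separate an average period effect from treatment. Bias needs change that differs between participants and that an investigator can foresee in people who have never worn a hearing aid. A shift of 0.5 SD is demanding: under normal selection it means turning away about 30% of candidates with perfect foresight, and about 62% if judgement correlates 0.5 with the later change.

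Two further inferences also fail. Converting the bias into IOI-HA points would use the SAP's 3.2 points and effect size 0.68, but these come from experienced users, who are excluded. Nor would steering be beyond all examination afterwards: enrolment logs are kept (Protocol 12.1.2), eligibility is verified for every participant (12.3), and baseline data are recorded.

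**Conclusion.** The point holds as a gap in allocation procedure. The plan discloses a fixed block size in an open trial, describes no concealment, and gives two block descriptions that do not agree. If blocks run within investigator, 22% to 33% of orders can be deduced and the best guess is right 67% to 71% of the time; under a common list seen only in part, predictability is slight.

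The risk to the result is modest. The 0.17 to 0.21 SD bias assumes within-investigator blocks, steering of 0.5 SD on future period change, and the same direction for all four investigators. None of these is shown. The cross-over removes stable differences, and the synopsis calls the analysis exploratory. A reader might conclude that entry will be steered or that the comparison is compromised; the documents support only that steering would be possible. The change is still worth making, because it is cheap before the first participant and hard to make good later.

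**What to change.** In Protocol 6.2.1 and 7.3:

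1. Reconcile the block of four with the 6 block design, and say whether blocks run within investigator. Keep the block size out of the protocol text.
2. State that the trial statistician generates and holds the list, using varying block sizes that are not disclosed to the sites.
3. State that the EDC system already planned (12.2) releases one order at a time, and only after that participant's consent, eligibility, audiogram and Gothenburg data are saved.

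Timed release matters most. Varying the sizes removes most certain knowledge: sizes of 4 and 6 mixed in one list of 24 leave about 5.7% certain, against 33.3% for fixed fours. It barely lowers the best-guess rate, which goes from 0.67 to 0.65 at 6 per investigator with sizes 4, 6 and 8. Release after eligibility is saved prevents direct sight of the next order and leaves a dated record of the entry decision. I would keep blocks of some kind, because the SAP relies on a balanced cross-over to control the period effect.

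The cost is wording in two sections, a small set-up task in the EDC system, and slight order imbalance from incomplete blocks. No extra visits or participants are needed.
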